### Baseline data:

- Patient
  - Age/Sex
  - o Baseline uncorrected and best-corrected visual acuity in operative eye
  - LOCS III cataract grade
  - Result of full ocular examination including test for afferent pupillary defect and intraocular pressure, with subsequent dilation of the pupil and B-scan in the event of inadequate visualization of the fundus
- Physician
  - Age/Sex
  - Presenting and best-corrected visual acuity in both eyes (near and distance)
  - Years of ophthalmic practice
  - Previous number of independent cataract surgeries performed (SICS and total)
  - Mean video grade across all steps on 3 successive SICS cases using ICO OSSCAR (Grader masked to surgeon/patient identity)

### The Intervention

All participants in both intervention and control groups will undertake the 2-4 week Orbis-COS STEER training course. This course will consist of didactic training, observation as well as a minimum of:

- 1) wet lab training with 50 pig eyes
- 2) assisting 30 surgeries, finishing one of more steps of the procedure, and
- 3) 50 independent operations under supervision.

Participants in the intervention group will be introduced to a variety of simulation-based surgical training techniques over 2 to 4 weeks. This additional training will involve a total of approximately 16 hours of video-based presentations, practical SICS procedures on model eyes, trainee feedback, and self-assessment of surgical performance using the simulation-OSSCAR scoring system. Specifically, this will involve breaking down the SICS cataract surgery procedure into stages. At each stage surgeons will be presented background knowledge and then practice that stage repeatedly using simulation. This sustained deliberate practice will be an enhancement to the STEER course, and not as a replacement of any part of the educational content. Within the first week of the course, 'intervention' arm participants will be introduced to the artificial eyes, practice the cataract surgery procedure using the Simulation-OSSCAR as a learning tool, and be provided with ongoing feedback. (See also Standard Operating Procedures (SOP) 9 through 19 for Model Eye Training).

It is excepted that surgeons will independently complete 8 SICS procedures by the end of the training period. The first two simulation SICS procedures on model eyes will be performed under supervision of the consultant trainer. The fourth and eighth SICS procedure will be recorded, uploaded to Cybersight, and assessed by PI [name] who will provide feedback to the trainee.

During this time, trainees in the control group are at liberty to spend time as they please.

Week	Knowledge & Understanding		SI [Practical skills lea wet-lab	kills arning & practice in / drv-labl	Attitudes & Assessment [Online, video-recording, and reflective learning]	
	Aim	Time / [Outcome]	Aim	Time / [Outcome]	Aim	Time / [Outcome]
1	Learning theory & expertise	20 minutes			Reflective learning	20 minutes
	Scleral tunnelling	20 minutes	Scleral tunnel	2 hours [perform 40 tunnels on apples]		
	Capsulotomy.	20 minutes	Capsulotomy	2 hours [perform 20 capulotomies on tomatoes, and 10 using Kitaro kit)		
	SICS video.	50 minutes			Introduction to SICS ICO-OSCAR	30 minutes
	Simulation SICS video	20 minutes	Initial artificial eye simulation surgery	2 hours [perform 3 full SICS]	Introduction to SICS Simulation-OSSCAR	20 minutes
2			Scleral tunnel	1 hours [perform 30 tunnels on apples]	Audit / Monitoring of outcomes	20 minutes
	Simulation SICS video	20 minutes	Artificial eye simulation surgery	3 hours [perform 5 full SICS]	SICS Simulation- OSSCAR: self- assessment	2 hours

#### **China-OLIMPICS Trial Intervention Objectives and Timetable**

#### Follow-up

### Participant Follow-up schedule:

Data collected at follow-up in the County Hospital:

• Surgical recording of ten live SICS procedures (supervised by the trainer).

### Patient Follow-up schedule: Post-op Day 1

Data at follow-up:

- Uncorrected and best-corrected visual acuity in operative eye (post-operative day (POD) 1)
- Ocular examination of operative eye with dilation of pupil to detect any co-morbidity undetected at baseline examination (POD 1)

### Analyses

#### Statistical Analysis

- Mean OSCAR grade for 10 consecutive consenting patients for each surgeon, comparing Intervention and Control Groups, with and without adjustment for baseline surgeon and patient factors. Each surgeon will have two mean OSCAR grades, one based off scores on all surgical steps and the other based off scores on trainee-completed steps, and they will be our co-primary outcomes. GEEs (generalised estimating equations) will be used for repeated measures analysis of the OSCAR scores.
- Mean presenting logMAR visual acuity on POD 1 for ten consecutive consenting patients per surgeon, comparing Intervention and Control Groups, with and without adjustment for baseline surgeon and patient factors.
- Mean improvement in lines of visual acuity in operative eye at POD 1, for 10 consecutive consenting patients per surgeon, comparing Intervention and Control Groups, with and without adjustment for baseline surgeon and patient factors.

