# Methodology

Study Design: Randomized controlled trial of an educational intervention.

Study Population: Cataract surgical trainees learning to perform small-incision cataract surgery (SICS) in the Orbis/Chinese Ophthalmic Society Rural Training Program (STEER). (This is a currently funded Orbis project, thus reducing the costs for this randomised trial.)

Partners: Orbis International and Queen's University Belfast ([name] is affiliated with both); Tongren Hospital and the Chinese National Committee for the Prevention of Blindness ([name] heads both); and International Centre for Eye Health at the London School of Hygiene & Tropical Medicine ([name], [name])

Sample Size Calculations: Based on OSCAR (ophthalmology surgical competency assessment rubric) scores for different surgical steps among SICS trainees at Aravind, India: 14 doctors in each of two groups operating on 10 patients each (total 280 surgeries) would allow for detection of a difference in mean OSCAR scores (across all steps) of 1.0 (point per set) between groups with a power of 0.9, alpha-error of 0.05, a standard deviation of 1.0 for scores, and an ICC of 0.57 for scores across cases within surgeon. The ICC value comes from our review of SICS cataract surgical training assessed using OSCAR in other Orbis training programs. (As this main outcome will be captured during surgery, there is no need to inflate our required sample size estimate to allow for loss to follow-up).

A total of 34 participants has been selected, to allow for a 15% attrition rate.

ICO-OSCAR scores cover 19 categories, with each category score ranging 0 to 5, and therefore with an overall 0 to 95. An example of a 1.0 point difference within the category, "Conjunctival and Corneal Tissue Handling" is for a Competent score (score = 5) the "tissue is not damaged nor at risk by handling," while for an Advanced Beginner score (score = 4), "tissue handling decent but potential for damage exists."

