### Outcomes

Main outcome: Mean video grade of the first 10 successive supervised or assisted SICS cases (with patient consent) for each surgeon, using ICO-OSCAR. Two approaches to determine mean video grade will be employed to account for the variation in the number of surgical steps performed by trainees. Variation either arises from individual competence, with the assumption that more competent surgeons are given a larger role during surgery, or from the teaching style of different mentors, with an emphasis on conservative training.

Both approaches are equally significant for determining the main outcome, and differ solely in the number of steps graded.

- Mean video grade across all surgical steps of the first 10 successive supervised or assisted SICS cases (with patient consent) for each trainee surgeon, using ICO-OSCAR. This approach penalizes surgeons for executing less steps, assigning a score of 0 for steps not performed.
- Mean video grade across all trainee-completed steps of the first 10 successive supervised or assisted SICS cases (with patient consent) for each trainee surgeon, using ICO-OSCAR. This approach scores surgeons only on surgical steps they performed in consideration of the variation in mentors' teaching styles.

The graders are masked to surgeon/patient identity, using a file-sharing platform to transfer videos to graders and collate grading information. These 10 cases will be the first 10 out of 30 cases completed under the supervision of the STEER traine.

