#### Randomisation (stratified blocked randomization):

Participants who have reached the appropriate inclusion and exclusion criteria for the trial will be eligible for randomisation to 'intervention' or 'control'.

Eligible trainees completing baseline data collection will be enrolled into the study and stratified into 10 groups\* according to their training center and hospitals (home facilities). The hospitals with only one participant are combined to form a mixed group. Participants in each of the 10 stratified groups will be assigned at random to one of the study arms as shown in the following figure.

An independent statistician having no contact with participants will generate the randomization sequences (lists) using a computer system that is inaccessible until after recruitment. The random sequence includes three types: (1) A list of the mixed hospitals with only one participant; (2) A number of lists of the hospital with paired participants (3) Individual list(s) of the hospitals with more than two participants. Each random sequence comprises of sequence numbers and their corresponding codes (e.g. two letters plus a 4-digit number). Codes are used to represent the Intervention or Control group; a codebook is created for decoding the group allocations.

To preserve allocation concealment, a two-step procedure will be used for random allocation in each training center.

**Step 1**: Project manager (PM) sends randomization sequences to the Quality Control officer (QCO). QCO assigns a code to each participant from the randomization sequences. QCO update the random lists with participant's names and send it to PM. At the end of this step, neither the QCO or participants know what group the codes refer to.

**Step 2:** As soon as receiving result file from QCO, PM checks the codebook, update the file with participant's names and send it back to QCO. QCO allocates the participants into control and intervention groups and completes the random allocation.

The participants will know their group assignment. However, the staff(s) grading video recordings of assessments will be masked by having a randomized number assigned to each video.

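### The OSCAR analysis ignores the 10 randomisation strata and names no small-sample standard error, so the level of the primary test depends on an unstated choice

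*Combined protocol and SAP*

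**What the plan says.** The Randomisation section forms 10 strata from training centre and home hospital: "Participants in each of the 10 stratified groups will be assigned at random to one of the study arms". It adds that "The hospitals with only one participant are combined to form a mixed group".

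The Statistical Analysis section states that "GEEs (generalised estimating equations) will be used for repeated measures analysis of the OSCAR scores", comparing the arms "with and without adjustment for baseline surgeon and patient factors". It does not list those factors. It gives no stratum, centre or hospital term, no type of standard error, no small-sample correction and no reference distribution. The list of baseline data for physicians contains neither centre nor hospital. Prevention of Bias mentions only baseline OSCAR score and number of previous cases.

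On numbers, the sample size paragraph plans 14 surgeons per arm with 10 cases each, then says: "A total of 34 participants has been selected, to allow for a 15% attrition rate".

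**The concern.** Stratified randomisation removes stratum differences from the comparison of arms. An analysis that ignores the strata leaves those differences in its error term, so its standard error is too wide when strata matter. Separately, the usual GEE sandwich standard error is too small with about 30 clusters. The two errors pull in opposite directions, and the plan controls neither. Whether the result is conservative or liberal depends on a stratum effect that nobody knows in advance and on a software default that is not stated.

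There is some reason to expect stratum effects. The graded cases are recorded in the county hospital with the trainer supervising. The Outcomes section says the number of steps a trainee performs varies with competence or "from the teaching style of different mentors, with an emphasis on conservative training". That bears mainly on the all-steps score, where a step not performed scores 0.

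**Working it through.** **Inputs from the sample size paragraph:** SD 1.0, ICC 0.57, 10 cases per surgeon, 14 surgeons per arm, difference 1.0, alpha 0.05, power 0.9, 34 surgeons after 15% attrition. **From Randomisation:** 10 strata. **Assumed:** a two-sided test, the stratum sizes, and the share *s* of between-surgeon variance explained by strata (0, 10, 20, 30%).

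**1. The plan's own figure.** Design effect = 1 + 9 × 0.57 = 6.13. Unclustered n per arm = 21.01, so 21.01 × 6.13 / 10 = 12.88 surgeons. Rounding 21.01 up to 22 first gives 22 × 6.13 / 10 = 13.49, hence 14. The noncentral t gives power 0.878 at 13 and 0.902 at 14. Then 14 / 0.85 = 16.5, so 17 per arm and 34 in all. The stated figures reproduce.

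**2. How far the standard error is off.** Variance of a surgeon's mean = 0.57 + 0.43/10 = 0.613, so the SE of the difference is √(2 × 0.613/14) = 0.296. With arms balanced within strata, the stratum part cancels and the true SE is √(2 × (0.613 − 0.57*s*)/14):
- *s* = 10%: 0.282, ratio 1.05
- *s* = 20%: 0.267, ratio 1.11
- *s* = 30%: 0.251, ratio 1.18

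Simulation gives an excess of about 0/4/10/17% with 28 surgeons and none lost. It is slightly lower because surgeons in the same arm can share a stratum. With 34 losing 6 at random it is 0/3/7/12%.

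**3. Type I error at nominal 0.05.** Surgeon means were simulated, 10,000 runs per setting (Monte Carlo SE 0.002). With equal numbers of cases, exchangeable GEE with the sandwich SE equals the HC0 formula on surgeon means; fitted examples confirmed this. Layouts: 28 = 6, seven pairs, 4, 4; 34 = 6, seven pairs, 7, 7. Four values in a cell are for *s* = 0/10/20/30%.

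| Analysis | 28, none lost | 34, losing 6 |
|---|---|---|
| No strata, uncorrected sandwich, 1.96 | 0.069/0.060/0.049/0.038 | 0.069/0.060/0.052/0.044 |
| No strata, t-type or corrected SE | 0.049/0.042/0.033/0.025 | 0.049/0.042/0.035/0.031 |
| Random stratum intercept, REML, t | 0.046-0.057 | 0.046-0.057 |
| Fixed strata, bias-corrected SE | 0.046-0.054 | 0.046-0.054 |
| Fixed strata, uncorrected sandwich | 0.14-0.15 | 0.13-0.14 |

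Other layouts (a mixed group of 8 or 10, or nearly even strata) gave the same pattern. With all 34 surgeons retained, fixed strata with an uncorrected sandwich gave 0.114-0.124. Fixed strata with a t test on residual df gave 0.045-0.053. At a more extreme share of 50%, the uncorrected sandwich without strata fell to 0.017-0.024.

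**4. Power after losing 6 of 34**, for *s* = 0/10/20/30%. The 0.7-point difference is assumed; 1.0 is the plan's.

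| Analysis | 0.7 points | 1.0 point |
|---|---|---|
| No strata, corrected SE | 0.62/0.62/0.64/0.65 | 0.90/0.91/0.92/0.93 |
| Random stratum intercept | 0.63/0.65/0.69/0.74 | 0.90/0.92/0.94/0.96 |
| Fixed strata, corrected SE | 0.55/0.59/0.64/0.69 | 0.85/0.87/0.91/0.94 |

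**The case against.** The strongest reply is that the plan's default reading does little harm. GEE with its usual sandwich SE and no strata stays within about 0.02 of 0.05 over the assumed shares, because the two errors partly offset. Against that test, modelling strata gains no power below a share of about 20-25%. This stands, and it limits the weight of the point. It does not remove it: the offset is close only near a 20% share, which cannot be known beforehand, and a corrected SE without strata loses the offset and becomes conservative.

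Four stronger readings are tempting but not supported:
- *The plan's test has a type I error of 0.11-0.15.* That belongs to strata added to an uncorrected sandwich GEE, which the plan does not propose.
- *The estimate is biased or the trial is underpowered.* Neither follows: randomisation within strata protects the estimate, and power at 1.0 point is 0.90-0.93 without strata.
- *Mentor effects are stratum effects.* No section says that one mentor serves one stratum. The description of control training has a training-centre surgeon travelling to mentor the trainee, which fits variation between trainees equally well, and clustering by surgeon already absorbs that. The second co-primary score also allows partly for mentor style: "This approach scores surgeons only on surgical steps they performed in consideration of the variation in" how mentors teach.
- *Visual acuity is affected in the same way.* The documents give no SD, ICC or stratum effect for acuity.

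It may also be said that the baseline surgeon factors could include hospital. Nothing says so, and the version without adjustment would still omit it.

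**Conclusion.** The point holds as a cheap improvement. The randomisation uses 10 strata, the OSCAR analysis uses none, and no small-sample test is named for 28 to 34 surgeons. Depending on the SE chosen, the level without strata runs from about 0.07 to 0.04 (uncorrected sandwich) or from about 0.05 to 0.025-0.035 (t-type or corrected) as the stratum share goes from 0 to 30%. That the text leaves this open is certain. The size rests on assumed stratum sizes and shares, since the documents give neither.

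Two related matters stay open whatever is done here: the plan gives no success rule for the two co-primary scores, and it does not say whether the adjusted or the unadjusted result is primary.

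**What to change.** In the Statistical Analysis section, for both co-primary OSCAR scores, state that the surgeon is the cluster and that the randomisation stratum is accounted for with a valid small-sample test, in the versions with and without adjustment alike.

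- **Preferred:** random intercepts for stratum and surgeon, fitted by REML, with a t reference on surgeons − strata − 1 df (28 − 10 − 1 = 17). If strata are uninformative this costs no measurable power (0.63 against 0.62 at 0.7 points; 0.90 against 0.90 at 1.0). At a 30% share it gains about 9 to 10 points at 0.7. The gain shrinks to about 7 or 4 points if hospitals inside a mixed group of 6 or 12 also differ.
- **Acceptable:** strata as fixed effects, with a t test on residual df using surgeon means, or GEE with a Bell-McCaffrey SE and Satterthwaite df. If strata are uninformative and 6 of 34 are lost, power at 1.0 point is about 0.85 rather than 0.90. An HC3-type SE is too conservative here (type I error 0.012-0.020).
- **Avoid:** adding the 10 strata to a GEE with an uncorrected sandwich SE, where type I error is about 0.11-0.15 depending on retention and layout.

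The cost is wording, plus the power loss noted if fixed strata are chosen. No surgeons or data are added. The same model may be used for visual acuity for consistency only. Which baseline covariates to adjust for is a separate decision.

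### Two equally weighted co-primary OSCAR outcomes have no decision rule, while alpha, power and sample size are set for one of them only

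*Combined protocol and SAP*

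**What the plan says.** The Outcomes section defines the main outcome in two ways from the same ten videos per surgeon. One mean counts a step that the trainee did not perform as zero. The other leaves such steps out. The section gives them equal standing: "Both approaches are equally significant for determining the main outcome, and differ solely in the number of steps graded". The Statistical Analysis section repeats this, with "one based off scores on all surgical steps and the other based off scores on trainee-completed steps, and they will be our co-primary outcomes". It plans GEE for the OSCAR scores and a comparison of arms both adjusted and unadjusted for baseline surgeon and patient factors, without saying which is primary.

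The Sample Size Calculations paragraph under Methodology contains one calculation. Its target is "detection of a difference in mean OSCAR scores (across all steps) of 1.0 (point per set", so it concerns the all-steps mean. It is made "with a power of 0.9, alpha-error of 0.05, a standard deviation of 1.0 for scores". The within-surgeon ICC is taken as 0.57. It arrives at 14 surgeons per group with 10 cases each, and 34 surgeons are selected to allow for 15% attrition.

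The document gives no rule for combining the two outcomes, no split of alpha, no testing order, and no effect size, SD or ICC for the completed-steps mean.

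**The concern.** With two primary outcomes of equal rank, the reader needs to know in advance what counts as a positive trial. Here that choice is open until the results are known. If a significant result on either outcome may carry the claim, the chance of a false positive exceeds the stated 0.05. If both must be significant, or if alpha is divided, the stated power of 0.9 was not calculated for that test. Adjusted and unadjusted versions of each outcome give 2 x 2 = 4 p-values, any of which could be presented as the primary result.

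The two means can also diverge. The Outcomes section assumes that a more competent trainee may be given more of the operation. Extra steps replace zeros in the all-steps mean, but they enter the completed-steps mean at whatever grade they earn. If the two results differed, the plan would not say which one answers the trial's question.

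**Working it through.** **Inputs from Sample Size Calculations:** difference 1.0, SD 1.0, ICC 0.57, 10 cases per surgeon, alpha 0.05, power 0.9, 14 surgeons per arm, 15% attrition.

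**Assumptions made here:** two-sided tests (sidedness is not stated; a one-sided test would need only 11 per arm, so two-sided fits the stated figure); the same 1.0 effect and the same SD and ICC for the completed-steps mean; a correlation between the two surgeon-level means, varied from 0 to 0.9; an equal split of the 34 surgeons.

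**Step 1: reproduce the plan's figure.**
- Design effect = 1 + (10 - 1) x 0.57 = 6.13.
- Variance of a surgeon's mean = 6.13 / 10 = 0.613, so SD = 0.783.
- Independent cases per arm = 2 x (1.960 + 1.282)^2 = 21.01. Surgeons per arm = 21.01 x 6.13 / 10 = 12.88. Rounding 21.01 up to 22 first gives 22 x 6.13 / 10 = 13.49, hence 14.
- t-test on surgeon means at 14 per arm: standard error = 0.783 x sqrt(2/14) = 0.296; noncentrality = 1.0 / 0.296 = 3.38; 26 df; power = 0.902.
- Attrition: 14 / 0.85 = 16.5, so 17 per arm, 34 in all.

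The stated 14 and 34 are reproduced. The 0.902 is for one outcome and leaves almost no margin.

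**Step 2: apply the possible rules to two outcomes at 14 per arm.** Type I error for the either rule comes from the bivariate normal distribution; at independence it is 1 - 0.95^2 = 0.0975, which is the maximum. Power comes from simulation of two correlated t-tests (100,000 runs per correlation, simulation standard error about 0.001).

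| Correlation (assumed) | Either suffices at 0.05: type I error | Both required at 0.05: power | Bonferroni 0.025 each: power for at least one |
|---|---|---|---|
| 0 | 0.0975 | 0.814 | 0.973 |
| 0.3 | 0.0951 | 0.825 | 0.954 |
| 0.5 | 0.0907 | 0.835 | 0.936 |
| 0.7 | 0.0835 | 0.847 | 0.913 |
| 0.9 | 0.0704 | 0.871 | 0.882 |

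Bonferroni power for each outcome taken singly, by t-test at 0.025, is 0.834.

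**Step 3: repeat with all 17 per arm analysed.** Power for one outcome at 0.05 is 0.9505. Power for both is at least 0.9505^2 = 0.903, the value at independence, and rises with positive correlation. Bonferroni power per outcome is 0.909.

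**The case against.** The strongest reply is that co-primary is often understood to mean that both outcomes must succeed. Type I error is then controlled and only power is in question. The power losses above are at 14 per arm, yet 34 surgeons are selected; if all 17 per arm are analysed, both-required power is at least 0.90. Bonferroni also looks better when judged on winning at least one outcome: 0.88 to 0.95 at 14 per arm for correlations of 0.9 to 0.3. The plan has a reason for keeping both scores, since the number of steps performed may reflect the trainee's competence or the mentor's style.

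Much of this stands, and it limits the claim. It does not supply the rule. The document never says that both are required, and calling the two scores equally significant does not settle it. The additional surgeons are there to cover attrition, so the design's 0.9 rests on 14 per arm. A reason for measuring both scores is not a rule for deciding between them.

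Three stronger readings are tempting, and the document does not support them:
- A reader might infer that type I error is nearly doubled. That is the value at independence. Both scores come from the same videos and share every performed step, so a positive correlation is likely, although no figure is given.
- A reader might infer that the plan must lose either its alpha or its power. A single primary outcome followed by an ordered test loses neither.
- A reader might infer that the two scores will point in opposite directions. The scoring makes this possible, but any numerical example needs invented step grades and a choice about how the six global indices in Appendix 3a are scored, so it can only be illustrative.

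**Conclusion.** The concern holds as a missing decision rule for the primary conclusion. It does not show that the error rate is inflated under every reading of the plan. If either outcome suffices at 0.05, type I error is about 0.07 to 0.09 for correlations of 0.9 down to 0.5, or 1.4 to 1.8 times nominal. If both are required, type I error is controlled and power at 14 per arm is about 0.81 to 0.87 for correlations of 0 to 0.9. With Bonferroni, power is 0.83 per outcome at 14 per arm and 0.91 at 17.

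The power figures assume a true 1.0-point effect and the same SD and ICC on both outcomes, which the document states only for the all-steps mean. The correlations are assumed throughout. No error rate has been calculated for the choice between adjusted and unadjusted models; those results will be closely related, but that choice is open too.

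**What to change.** In Outcomes and Statistical Analysis, before any results are compared by arm, make the all-steps mean the single primary outcome at 0.05, because the sample size was built on it. Test the completed-steps mean, also at 0.05, only if the primary is significant. This holds the overall error at 0.05 and keeps the stated 0.90 for the primary.

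If both are to remain co-primary, state either that both must be significant or that Holm or Bonferroni will be used. Then restate the power in Sample Size Calculations to match, with an effect size, SD and ICC for the completed-steps mean and an assumed correlation.

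In either case, name one model, adjusted or unadjusted, as primary for each outcome and report the other as supportive. Modelling individual step scores so that arms are compared on the same steps is optional. It would change the outcome as defined, and the decision rule does not need it.

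The cost is wording only, with no extra patients or data. The completed-steps mean loses its equal standing, or else the stated power becomes somewhat less favourable.
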